## 7.2. Safety Analyses

The safety analyses will be based on the ITT population, unless otherwise specified. The summaries will be presented based on the AEs during on-treatment period. The listings will be presented based on the AEs during entire study. On-treatment is defined in the Appendix 3.

### 7.2.1. Overview of Planned Adverse Event Analyses

Table 5 provides an overview of the planned analyses, with further details of data displays being presented in Appendix 10: List of Data Displays.

**Table 5      Overview of Planned Adverse Event Analyses**

Endpoint / Parameter/ Display Type	Absolute		
	Summary		Individual
	T	F	L
Adverse Events (AEs)			
All AEs by SOC and PT	Y		Y
All AEs by SOC and PT and Maximum Intensity	Y		
AESI	Y		
AESI – Serious Infections and Non Serious Pulmonary or Opportunistic Infections			Y
AESI – Systemic Hypersensitivity Reactions			Y
AESI – Injection Site Reaction			Y
Adverse Events by Overall Frequency	Y		
Drug-Related AEs by SOC and PT	Y		
Drug-Related AEs by SOC and PT and Maximum Intensity	Y		
Common Non-Serious Adverse Events by SOC and PT	Y		
Subject Numbers for Individual AEs			Y
Relationship Between AE SOCs, PT and Verbatim Text			Y
AEs Leading to Withdrawal from Study	Y		
AEs Leading to Permanent Discontinuation of Study Treatment	Y		
AESI Leading to Permanent Discontinuation of Study Treatment	Y		
Disease Related Events	Y		Y
Serious AEs			
Serious AEs			Y
Serious AEs by SOC and PT	Y		

**NOTES:**

- T = Table, F = Figures, L = Listings, Y = Yes display generated, SOC = System Organ Class, PT = Preferred Term.
- Summary = Represents TF related to any summaries (i.e. descriptive statistics) of the observed raw data.
- Individual = Represents FL related to any displays of individual subject observed raw data.

## **8.      SECONDARY STATISTICAL ANALYSES**

### **8.1.      Safety Analyses**

#### **8.1.1.      Overview of Planned Other Safety Analyses**

The safety analyses will be based on the ITT population, unless otherwise specified.

Table 6 provides an overview of the planned analyses, with further details of data displays being presented in Appendix 10: List of Data Displays.

**Table 6 Overview of Planned Other Safety Analyses**

Endpoint / Parameter/ Display Type	Absolute			Change from BL		
	Summary		Individual	Summary		Individual
	T	F	L	T	F	L
ECG						
ECG Findings	Y					
Change from Baseline in ECG Values by Visit				Y		
ECG values by Visit	Y		Y			
Abnormal ECG Findings			Y			
Vital Signs						
Change From Baseline in Vital Signs by Visit				Y		
Vital Signs by Visit	Y		Y			
Pulmonary						
Cough by Visit and Grade	Y		Y			
Lung Auscultation by Visit	Y		Y			
Pulse Oximetry by Visit	Y		Y	Y		
Borg Dyspnea Scale by Visit	Y		Y			
FEV 1 by Visit	Y		Y	Y		
FVC by Visit	Y		Y	Y		
D LCO by Visit	Y		Y	Y		
Respiratory events						
Persistent cough with grade 2 or greater recorded	Y		Y			
Persistent dyspnea with grade 3 or greater recorded	Y		Y			
Persistent D LCO by >15%	Y		Y			
Hepatic B Virus						
HBV DNA monitoring			Y			

**NOTES:**

- T = Table, F = Figures, L = Listings, Y = Yes display generated,
- Summary = Represents TFL related to any summaries (i.e. descriptive statistics) of the observed raw data.
- Individual = Represents FL related to any displays of individual subject observed raw data.

**8.1.1.1. Pulmonary assessment**

All pulmonary assessment results (Cough, Lung Auscultation, Pulse Oximetry, Borg Dyspnea Scale, FEV1, FVC and DLCO) will be listed.

The values and the changes from baseline for the FEV1, FVC, DLCO and Pulse Oximetry will be summarized. The number and percentages of subjects having a cough for each grade and each Borg dyspnea scale will be summarized by visit.

### 8.1.1.2. Respiratory events

Numbers and percentages of subjects experiencing persistent cough, or persistent dyspnea or persistent DLCO decrease will be reported in a table by dose group at the start time of the event.

The definitions of these events are described in the Appendix 5.

### 8.1.2. Overview of Planned Clinical Laboratory Analyses

Table 7 provides an overview of the planned analyses, with further details of data displays being presented in Appendix 10: List of Data Displays.

If a subject fails any of the laboratory inclusion/exclusion criteria, laboratory test related to the inclusion/exclusion criteria may be repeated in screening period. The data collected by retests are not at screening visit but unscheduled visit. Therefore the summary at Screening visit will not be presented and baseline values defined in the Appendix 4 will be summarized.

**Table 7 Overview of Planned Clinical Laboratory Analyses**

Endpoint / Parameter/ Display Type	Absolute			Change from BL		
	Summary		Individual	Summary		Individual
	T	F	L	T	F	L
Chemistry						
Chemistry Changes from Baseline				Y		
Chemistry by visit	Y		Y			
Emergent Chemistry Results Relative to Normal Range	Y					
Hematology						
Hematology Changes From Baseline				Y		
Hematology by Visit	Y		Y			
Emergent Hematology Results Relative to Normal Range	Y					
Urinalysis						
Urinalysis Dipstick Results	Y		Y			
Hepatobiliary (Liver)						
Liver Monitoring/Stopping Event Reporting			Y 			
Hepatobiliary Laboratory Abnormalities	Y 					
Medical Conditions for Subjects with Liver Stopping Events			Y 			
Substance Use for Subjects with Liver Stopping Events			Y 			
Liver Monitoring/Stopping Event Reporting			Y 			
Liver Stopping Event Information for RUCAM Score			Y 			
Liver Biopsy Details			Y 			
Liver Imaging Details			Y 			

Endpoint / Parameter/ Display Type	Absolute			Change from BL		
	Summary		Individual	Summary		Individual
	T	F	L	T	F	L
Laboratory Tests (Antigen and Antibody) for Liver Events			Y 			
Laboratory Tests (DNA and RNA) for Liver Events			Y 			
Cardiovascular						
ECG Findings in Cardiovascular Events			Y 			
Subjects who had Cardiovascular Events			Y 			
Diagnostic Test for Cardiovascular Events			Y 			
Findings about Cardiovascular Events			Y 			
Healthcare Resource Utilization due to Cardiovascular Events			Y 			
NYHA Functional Class for Cardiovascular Events			Y 			
Death in Cardiovascular Events			Y 			

**NOTES:**

- T = Table, F = Figures, L = Listings, Y = Yes display generated
- Summary = Represents TFL related to any summaries (i.e. descriptive statistics) of the observed raw data.
- Individual = Represents FL related to any displays of individual subject observed raw data.
- RUCAM: Roussel Uclaf Causality Assessment Method
- [1]: if at least one Liver event occurs, this display will be presented.
- [2]: if at least one Cardiovascular event occurs, this display will be presented.

### 8.1.3. Immunogenicity Analyses

The immunogenicity analyses will be based on the Immunogenicity population, unless otherwise specified.

The positive subjects of Anti-GSK3196165 Binding Antibody Detection are defined as those of which tests at Confirming are “positive”, and otherwise negative. The positive subjects of Neutralising Antibody detection are defined those of which tests at Screening are “positive”, and otherwise negative.

The number and percentage of positive and negative subjects will be summarized. Shift table from baseline to every assessment will be produced to assess the number of subjects going from:

- negative→negative
- negative→positive
- positive→negative
- positive→positive

Anti-GSK3196165 Binding Antibody Detection (positive/negative) will be listed together with titre value (mL) and Rheumatoid Factor (positive/negative) for each subject with at least one positive result of Anti-GSK3196165 Binding Antibody Detection.

**Table 8 Overview of Immunogenicity Analyses**

[Endpoint / Parameter/ Display Type]	Absolute						
	Stats Analysis			Summary		Individual	
	T	F	L	T	F	F	L
Immunogenicity				Y			Y

**NOTES:**

- T = Table, F = Figures, L = Listings, Y = Yes display generated
- Stats Analysis = Represents TFL related to any formal statistical analyses (i.e. modelling) conducted.
- Summary = Represents TFL related to any summaries (i.e. descriptive statistics) of the observed raw data.
- Individual = Represents FL related to any displays of individual subject observed raw data.

**8.2. Efficacy Analyses****8.2.1. Overview of Planned Efficacy Analyses**

The secondary efficacy analyses will be based on the ITT population, unless otherwise specified.

Table 9 provides an overview of the planned efficacy analyses, with further details of data displays being presented in Appendix 10: List of Data Displays.

**Table 9 Overview of Planned Efficacy Analyses**

[Endpoint / Parameter/ Display Type]	Absolute							Change from Baseline						
	Stats Analysis			Summary		Individual		Stats Analysis			Summary		Individual	
	T	F	L	T	F	F	L	T	F	L	T	F	F	L
DAS28 (CRP)														
Values				Y			Y				Y	Y		Y
Longitudinal data analysis								Y	Y					
Dose response analysis at Week 12								Y	Y					

**NOTES :**

- T = Table, F = Figure, L = Listing, Y = Yes display generated.
- Stats Analysis = Represents TFL related to any formal statistical analyses (i.e. modelling) conducted.
- Summary = Represents TFL related to any summaries (i.e. descriptive statistics) of the observed raw data.
- Individual = Represents FL related to any displays of individual subject observed raw data.

**8.2.2. DAS28 (CRP)**

DAS28(CRP) values will be listed and summarized by dose group and nominal time. Mean and Median change from baseline versus time profile by dose group will be plotted.

### 8.2.2.1. Planned Efficacy Statistical Analyses

Statistical Analyses –Mixed Model with Repeated Measures–	
Endpoint(s)	

 
Change from baseline in DAS28 (CRP)
 
	
Model Specification	

 
This endpoint will be analyzed using a mixed-models repeated measures (MMRM) approach.
 
Analysis will include the following fixed effects: 
 
Dose group as a categorical variable
 
Visit as a categorical variable
 
Baseline DAS28(CRP) as a continuous variable
 
Dose-by-visit interaction
 
Visit-by-baseline interaction
 
 
 
An unstructured variance structure will be used to model the within-patient errors.
 
Analyses will be done with the MIXED Procedure in SAS, using the Kenward-Roger option to estimate denominator degrees of freedom and standard errors.
 
	
Model Checking & Diagnostics	

 
Refer to Appendix 8: Model Checking and Diagnostics for Statistical Analyses.
 
	
Model Results Presentation	

 
LSmeans for each dose will be presented along with the associated 95% CI.
 
Point estimates and their associated 95% CI will be calculated for the differences between each GSK3196165 dose group and Placebo (GSK3196165 – Placebo).
 
The primary treatment comparison will be the contrast between the GSK3196165 groups to placebo.
 
	

Statistical Analyses – Dose response Analysis –	
Endpoint(s)	

 
Change from baseline in DAS28 (CRP) at Week 12.
 
	
Model Specification	

 
The following non-linear models will be fitted exploratory.
 
	
$DAS28(CRP)_i = E_0 + \frac{E_{\max} Dose_i}{Dose_i + ED_{50}} + \varepsilon_i$	
$DAS28(CRP)_i = E_0 + \frac{E_{\max} Dose_i^B}{Dose_i^B + ED_{50}^B} + \varepsilon_i$	
$DAS28(CRP)_i = E_0 + E_1 \times Dose_i + \varepsilon_i$	

 
The notation in the formula is as below: 
 
Subscript i denotes i-th subject.
 
<math>E_0</math> : Response at dose 0 (placebo)
 
<math>E_{\max}</math> : Maximum effect (for reduction, <math>E_{\max} \leq 0</math>; for increase, <math>E_{\max} \geq 0</math>)
 
<math>ED_{50}</math> : Dose at which 50% of maximum effect is reached
 
 
 
	

Statistical Analyses – Dose response Analysis –
--

- $B$  : a slope factor
- $E_1$  : Coefficient of a linear model.
- $\varepsilon_i$  : Residual error following  $N(0, \sigma^2)$
- The dose will be set to zero for all placebo data.
- Starting values for the iterations will be chosen based on the observed data as appropriate. For example;
  - $E_0$  : Mean in Placebo
  - $E_{max}$  : Mean difference between 180 mg and Placebo (180 mg – Placebo)
  - $ED_{50}$  :  $90 (= (180 - 0) / 2)$
  - $B = 1$
- Each of the models will be fitted to the data and their fit compared using the Akaike information criteria (AIC).
- The model with the smallest AIC will be selected as the final model for inference.

Model Checking & Diagnostics
---

- Refer to Appendix 8: Model Checking and Diagnostics for Statistical Analyses.

Calculation procedure for the 95% CIs using a bootstrap method
---

- The 95% CIs will be calculated in accordance with the following procedure.
  1. Recreate the dataset by sampling with replacement from the original dataset by dose group.
    - Use a PROC SURVEYSELECT with SEED = 161216 to generate the bootstrap dataset
  2. Fit the final dose response model to the dataset in step 1. Estimate the parameters of interest  $\hat{\theta}_1$  and compute  $g(\hat{\theta}_1)$  {g is any arbitrary function.}
  3. Repeat steps 1-2, for  $b = 1, 2, \dots, B$  ( $B=10,000$ ) to obtain  $\hat{\theta}_1, \hat{\theta}_2, \dots, \hat{\theta}_B$  and compute  $g(\hat{\theta}_1), g(\hat{\theta}_2), \dots, g(\hat{\theta}_B)$ .
  4. Select 2.5% quantile of the  $\hat{\theta}_b$  and  $g(\hat{\theta}_b)$  as the lower limit and 97.5% quantile as the upper limit.

Model Results Presentation
-----------------------------------

- The result of the final model will be presented.
- The estimates of model parameters and their 95% CI will be presented.
- From the fitted model, predictive responses for each of the doses will be calculated along with 95% CI.
- The differences between each GSK3196165 dose and Placebo and their 95% CI will be calculated from the fitted model.
- A plot of the residuals versus predicted values will be examined to assess distributional assumptions.
- The results of the other models will be shown as only SAS outputs.

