9.4.4. Efficacy Analyses

The ITT population with observed case dataset will be used for efficacy analyses. Time course of the change from baseline in DAS28(CRP) will be analyzed by mixed model for repeated measurements (MMRM). The dose response analyses will be performed on the change from baseline in DAS28(CRP) at Week 12. Full details for all efficacy analyses will be given in the RAP.

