### 11.6.2. Handling of Missing Data

Element	Reporting Detail
General	
 
Missing data occurs when any requested data is not provided, leading to blank fields on the collection instrument : 
 
These data will be indicated by the use of a “blank” in subject listing displays. Unless all data for a specific visit are missing in which case the data is excluded from the table.
 
Answers such as “Not applicable” and “Not evaluable” are not considered to be missing data and should be displayed as such.
 
 
 

Binary variable	
 
Subjects with missing efficacy data or early withdrawal will be imputed as a failure (e.g. no DAS28(CRP) remission or no moderate/good EULAR response).
 

Continuous variable	
 
No imputation will be done.
 

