#### 11.10.4. Efficacy Tables

Secondary Efficacy: Tables					
No.	Population	IDSL / TST ID / Example Shell	Title	Programming Notes	Deliverable
DAS28(CRP)					
2.1.	ITT	EFF_T1	Summary of DAS28(CRP) Values		SAC
2.2.	ITT	EFF_T1	Summary of Change from Baseline in DAS28(CRP)		SAC
Statistical Analysis for DAS28(CRP) Comparison with Placebo					
2.3.	ITT	EFF_T2	Summary of Repeated Measures Analysis of Change from Baseline in DAS28(CRP)		SAC
Dose Response Analysis in DAS28(CRP)					
2.4.	ITT	EFF_T3 or EFF_T4	Summary of Results of Dose Response Analysis for Change from Baseline in DAS28(CRP) at Week 12	Statistician will select the final model among the three dose response models.	SAC

Exploratory Efficacy: Tables					
No.	Population	IDSL / TST ID / Example Shell	Title	Programming Notes	Deliverable
ACR 20/50/70 response					
2.5.	ITT	EFF_T5	Summary of ACR 20 Responses		SAC
2.6.	ITT	EFF_T5	Summary of ACR 50 Responses		SAC
2.7.	ITT	EFF_T5	Summary of ACR 70 Responses		SAC
DAS28(ESR)					
2.8.	ITT	EFF_T1	Summary of DAS28(ESR) Values		SAC
2.9.	ITT	EFF_T1	Summary of Change from Baseline in DAS28(ESR)		SAC
2.10.	ITT	EFF_T2	Summary of Repeated Measures Analysis of Change from Baseline in DAS28(ESR)		SAC
SDAI, CDAI and FACIT-Fatigue					
2.11.	ITT	EFF_T1	Summary of SDAI Values		SAC
2.12.	ITT	EFF_T1	Summary of CDAI Values		SAC
2.13.	ITT	EFF_T1	Summary of FACIT-Fatigue		SAC
2.14.	ITT	EFF_T1	Summary of Change from Baseline in SDAI		SAC
2.15.	ITT	EFF_T1	Summary of Change from Baseline in CDAI		SAC
2.16.	ITT	EFF_T1	Summary of Change from Baseline in FACIT-Fatigue		SAC
2.17.	ITT	EFF_T2	Summary of Repeated Measures Analysis of Change from Baseline in SDAI		SAC
2.18.	ITT	EFF_T2	Summary of Repeated Measures Analysis of Change from Baseline in CDAI		SAC
2.19.	ITT	EFF_T2	Summary of Repeated Measures Analysis of Change from Baseline in FACIT-Fatigue		SAC

Categorical DAS28(CRP) / DAS28(ESR) Response					
2.20.	ITT	EFF_T5	Summary of Categorical DAS28(CRP) Responses		SAC
2.21.	ITT	EFF_T5	Summary of Categorical DAS28(ESR) Responses		SAC
DAS28(CRP) / DAS28(ESR) Remission					
2.22.	ITT	EFF_T5	Summary of DAS28(CRP) Remission		SAC
2.23.	ITT	EFF_T5	Summary of DAS28(ESR) Remission		SAC
The other endpoints					
2.24.	ITT	EFF_T6	Summary of Swollen/Tender Joint Counts		SAC
2.25.	ITT	EFF_T6	Summary of Patient's Assessment of Arthritis Pain		SAC
2.26.	ITT	EFF_T1	Summary of Patient's Global Assessment of Arthritis		SAC

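### The exploratory Week 12 DAS28(CRP) dose-response models leave out the baseline covariate that the MMRM uses; adding it is a cheap, optional gain in precision

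*SAP*

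**What the plan says.** SAP 8.2.2.1 sets out two analyses of change from baseline in DAS28(CRP).

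- **MMRM.** The fixed effects are dose group, visit, dose-by-visit, "Baseline DAS28(CRP) as a continuous variable" and a visit-by-baseline interaction. The results go to Table 2.3 (SAP 11.10.4).
- **Dose response at Week 12.** "The following non-linear models will be fitted exploratory": a three-parameter Emax, a sigmoid Emax and a straight line. Each has an intercept, a function of dose and a residual, and no baseline term.

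For the second analysis, "The model with the smallest AIC will be selected as the final model for inference". Bootstrap step 2 reads "Fit the final dose response model to the dataset in step 1". Among the outputs, "The differences between each GSK3196165 dose and Placebo and their 95% CI will be calculated from the fitted model".

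Protocol 9.4.4 leaves the detail to the RAP and adds "The ITT population with observed case dataset will be used for efficacy analyses". For continuous variables SAP 11.6.2 says "No imputation will be done". SAP Appendix 8 adds only a residual plot for this analysis. Nothing else in the documents supplies a baseline term for these models or explains why there is none.

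**The concern.** A change score already contains baseline, but with its coefficient fixed at -1. If baseline and Week 12 values are less than perfectly correlated, change usually still depends on baseline. In the dose-response models that dependence stays in the residual. With about 10 subjects per arm this has two faces: chance baseline differences between arms move the fitted curve, and the baseline-related spread within arms widens its intervals. These are one loss of precision, not two.

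The selected curve is labelled as the model for inference and produces dose-placebo differences with 95% CIs. Tables 2.3 and 2.4 will then give Week 12 differences for the same trial, only one of them adjusted for baseline, and they can differ partly for that reason.

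**Working it through.** **The plan's own figures.** Protocol Table 4 has the only precision figures in the documents: exact 95% limits for 1, 2 and 3 adverse events among 10 subjects. They reproduce as 0.25%-44.50%, 2.52%-55.61% and 6.67%-65.25%, which match to rounding. No SD, correlation or precision is given for DAS28(CRP).

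**Inputs from the documents.** 10 subjects in each of four arms; doses 0, 45, 90 and 180 mg; the three models; AIC selection; a percentile bootstrap within dose group.

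**Assumed inputs.** Baseline to Week 12 correlation r = 0.3, 0.5, 0.7. Baseline/Week 12 SDs (s0/s1) of 1.0/1.0, 0.9/1.2 and 0.8/1.2; the last two allow for entry criteria that limit baseline from below (Protocol 5.1). Week 12 data are complete. The response is read as the change score, as the stated endpoint says, although the formulas print DAS28(CRP) on the left-hand side.

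**Step 1: formula for the linear model.** Residual variance without baseline is s0² + s1² - 2·r·s0·s1. With baseline it is s1²(1 - r²). Estimating one more coefficient multiplies the variance by 1 + 1/36 = 37/36.

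- SDs 1.0/1.0, r = 0.3: 0.91/1.40 × 37/36 = 0.67.
- SDs 0.9/1.2, r = 0.5: 1.08/1.17 × 37/36 = 0.95.
- SDs 0.8/1.2, r = 0.7: 0.7344/0.736 × 37/36 = 1.03.

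**Step 2: the full procedure by simulation.** There were 20,000 runs per case. The assumed truth was either an Emax curve (maximum -1.2, ED50 60 mg) or a straight line reaching -0.9 at 180 mg. All three models were fitted with and without baseline, with ED50 searched over 5-1000 mg and the slope factor over 0.5-8. The smallest AIC was selected, with AIC = 40·ln(RSS/40) + 2k and k = 3, 4 or 5, plus 1 with baseline.

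Variance of the 180 mg minus placebo difference, adjusted divided by unadjusted:

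| SDs (baseline/Week 12) | Truth | r = 0.3 | r = 0.5 | r = 0.7 |
|---|---|---|---|---|
| 1.0/1.0 | Emax | 0.65 | 0.75 | 0.87 |
| 1.0/1.0 | linear | 0.66 | 0.76 | 0.87 |
| 0.9/1.2 | Emax | 0.83 | 0.95 | 1.02 |
| 0.9/1.2 | linear | 0.82 | 0.95 | 1.02 |
| 0.8/1.2 | Emax | 0.89 | 0.99 | 1.02 |
| 0.8/1.2 | linear | 0.89 | 0.99 | 1.03 |

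The range is -35% to +3% at 180 mg, -30% to +4% at 90 mg and -28% to +4% at 45 mg. A separate simulation of 8,000 runs per case agreed within about 0.03 at 180 mg. Its mean estimates with and without baseline differed by at most 0.017, so with complete data the cost is precision and not bias.

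**Step 3: interval width.** This used 2,000 datasets per case and 500 resamples (the SAP plans 10,000). Under the Emax truth, mean widths at 180 mg, adjusted divided by unadjusted, were 0.82/0.88/0.94, 0.92/0.98/1.02 and 0.95/1.00/1.02 for the three SD pairs, each at r = 0.3/0.5/0.7. Over all doses and both truths the range was 0.82 to 1.03.

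**Step 4: chance imbalance, linear fit, SDs 0.9/1.2.**

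- The slope of change on baseline is r × 1.2/0.9 - 1 = -0.60, -0.33, -0.07.
- The dose sum of squares about the mean of 78.75 mg is 17718.75 per set of four doses.
- The SD of a chance baseline trend over 180 mg is 0.9 × 180/√(10 × 17718.75) = 0.385.
- A 1-SD trend therefore shifts the 180 mg difference by 0.23, 0.13 or 0.03 units, and the 45 mg difference by a quarter of that.

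**Step 5: effect on model choice.** The AIC-selected model differed between adjusted and unadjusted fits in 4.9%-20.5% of runs (Emax truth) and 3.0%-12.3% (linear truth).

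**Outside the grid.** If the Week 12 SD were 0.8 times the baseline SD, a comparison of arm means gives unadjusted intervals 39%, 30% and 24% wider than adjusted ones at r = 0.3, 0.5 and 0.7. If the response really were the raw Week 12 score, the large-sample SE ratio would be √(1 - r²) = 0.95, 0.87 and 0.71, so the loss would grow with r.

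**The case against.** The strongest reply is that this is a modelling preference. No text requires the exploratory curve and the MMRM to share covariates. An intercept, a dose function and an error form a coherent model, and the change score already uses baseline with a fixed slope. All of that stands, and it is why the gain shrinks as the correlation rises.

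The size is assumed throughout. In the two SD pairs tied to the entry criteria, four of six cells (r of 0.5 or more) show a gain of 5% of variance or less, or a loss of up to 4%. The -35% needs equal SDs and r = 0.3. That also stands.

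Adjusted contrasts are already planned in Table 2.3, no hypothesis is tested, and the sample size rests on feasibility. So no planned conclusion changes.

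Nor does adjustment cure dropout bias. In a two-arm check with dropout driven by Week 8 DAS28 and a true difference of -0.9, the observed-case estimate was -0.83 unadjusted and -0.81 adjusted. The case for the term is therefore precision alone. The absence of bias holds only if Week 12 data are complete, or missing in a way that does not depend on arm and baseline together.

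Finally, the change touches the meaning of E0, the starting values, the centring constant and two listing titles. These are small edits and leave the definition of the dose-placebo contrasts unchanged. None of these points explains why the covariate is used in one analysis and not in the other.

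**Conclusion.** The point holds as an optional improvement. All three Week 12 dose-response models omit baseline DAS28(CRP), while the MMRM of the same endpoint includes it, and no reason is given. The cost is a modest loss of precision that depends on unknown inputs. Within the assumed grid, adjustment changes variance by -35% to +4% across the three doses. The gain is clear when baseline and Week 12 SDs are similar. It is near nil or slightly negative when the Week 12 SD is clearly larger and the correlation is 0.5 or more. The primary PK and safety analyses are unaffected.

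**What to change.** Add one common term, γ × (subject's baseline DAS28(CRP) minus the overall mean baseline), to each of the three models before the AIC comparison. Predict at the overall mean baseline and re-estimate γ in every bootstrap resample. Alternatively, state in one sentence why baseline is left out.

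The wording that follows from this:

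- define E0 as the placebo response at mean baseline;
- give γ a starting value;
- say whether the centring mean is held fixed across resamples. This affects the intervals for predicted responses, not the dose-placebo differences;
- correct the parameter counts in the titles of Listings 78 and 79.

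Settle this before unblinding, because the selected curve can change (3% to 21% of simulated runs). No new data are needed. The statistical cost is one residual degree of freedom, and about 3% more variance (up to 4% at 45 and 90 mg) if baseline explains almost none of the change. The AIC penalty rises equally in all three models. Convergence of the larger sigmoid model over 10,000 resamples was not examined without bounds on ED50 and the slope factor, and the SAP sets no such bounds.

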4. STUDY DESIGN

4.1. Overall Design

- This is a randomized, double-blind, parallel group, 3 dosage level, placebo-controlled, Phase 1/2 study with the objective to assess pharmacokinetics, safety, tolerability and efficacy of GSK3196165 for 12 weeks, in combination with methotrexate (MTX), in Japanese subjects with active moderate-severe RA despite treatment with MTX.
- Approximately 40 subjects will be randomized into the study (10 subjects in each treatment groups).

Figure 1 Study Design

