9.2. Sample Size Assumptions

The sample size is determined based on feasibility. A total of 40 subjects will be randomized in a 1:1:1:1 proportion to receive GSK3196165 doses of 45 mg, 90 mg, 180 mg or placebo.

[Table 4](#) provides the precision of percentage of subjects with specific adverse events in each group with 10 subjects.

Table 4 Precision of percentage of subjects with specific adverse events in each group with 10 subjects

Number of subjects	Number of particular safety events observed	Exact 95% confidence intervals
10	1	0.3% - 44.5%
10	2	2.5% - 55.6%
10	3	6.7% - 65.2%

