### 11.10.5. Efficacy Figures

Secondary Efficacy: Figures					
No.	Population	IDSL / TST ID / Example Shell	Title	Programming Notes	Deliverable
DAS28(CRP)					
2.1.	ITT	EFF_F3	Plot of Mean (95%CI) Change from Baseline in DAS28(CRP) Profiles		SAC
2.2.	ITT	EFF_F3	Plot of Median (Range) Change from Baseline in DAS28(CRP) Profiles		SAC
Statistical Analysis for DAS28(CRP) Comparison with Placebo					
2.3.	ITT	EFF_F3	Plot of Predicted (95%CI) Treatment Difference from Placebo in DAS28(CRP)		SAC
Dose Response Analysis in DAS28(CRP)					
2.4.	ITT	EFF_F2	Plot of Predicted (95%CI) Change from Baseline in DAS28(CRP) by the final Dose Response Model at Week 12	Statistician will select the final model among the three dose response models.	SAC
2.5.	ITT	EFF_F1	Plot of the Residuals versus the Predicted DAS28(CRP) by final Dose Response Model at Week 12		SAC

Exploratory Efficacy: Figures					
No.	Population	IDSL / TST ID / Example Shell	Title	Programming Notes	Deliverable
ACR20/50/70					
2.6.	ITT	EFF_F4	Barplot of ACR20 Response Rate by Visit		SAC
2.7.	ITT	EFF_F4	Barplot of ACR50 Response Rate by Visit		SAC
2.8.	ITT	EFF_F4	Barplot of ACR70 Response Rate by Visit		SAC
DAS28(ESR)					
2.9.	ITT	EFF_F3	Plot of Mean (95%CI) Change from Baseline in DAS28(ESR) Profiles		SAC
2.10.	ITT	EFF_F3	Plot of Median (Range) Change from Baseline in DAS28(ESR) Profiles		SAC
Statistical Analysis for DAS28(CRP) Comparison with Placebo					
2.11.	ITT	EFF_F3	Plot of Predicted (95%CI) Treatment Difference from Placebo in DAS28(ESR)		SAC
SDAI, CDAI and FACIT-Fatigue					
2.12.	ITT	EFF_F3	Plot of Mean (95%CI) Change from Baseline in SDAI Profiles		SAC
2.13.	ITT	EFF_F3	Plot of Median (Range) Change from Baseline in SDAI Profiles		SAC
2.14.	ITT	EFF_F3	Plot of Mean (95%CI) Change from Baseline in CDAI Profiles		SAC
2.15.	ITT	EFF_F3	Plot of Median (Range) Change from Baseline in CDAI Profiles		SAC
2.16.	ITT	EFF_F3	Plot of Mean (95%CI) Change from Baseline in FACIT-Fatigue Profiles		SAC
2.17.	ITT	EFF_F3	Plot of Median (Range) Change from Baseline in FACIT-Fatigue Profiles		SAC

Exploratory Efficacy: Figures					
No.	Population	IDSL / TST ID / Example Shell	Title	Programming Notes	Deliverable
Statistical Analyses for SDAI, CDAI and FACIT-Fatigue Comparisons with Placebo					
2.18.	ITT	EFF_F3	Plot of Predicted (95%CI) Treatment Difference from Placebo in SDAI		SAC

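### The exploratory Week 12 dose-response fit puts no stated limit on ED50, so a smallest-AIC Emax model can report a negative dose as its ED50

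*SAP*

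**What the plan says.** SAP 8.2.2.1 (Dose response Analysis) lists three models for the Week 12 change in DAS28(CRP). It gives example starting values, among them ED50 = 90 mg and B = 1, and a selection rule: "Each of the models will be fitted to the data and their fit compared using the Akaike information criteria (AIC"; the smallest value wins. ED50 is defined as "Dose at which 50% of maximum effect is reached". The only sign remark concerns Emax, which may be negative or positive according to direction.

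For intervals, each of 10,000 bootstrap samples repeats the fit: "Fit the final dose response model to the dataset in step 1". On output, "The estimates of model parameters and their 95% CI will be presented", and Figure 2.4 in SAP 11.10.5 is titled "Plot of Predicted (95%CI) Change from Baseline in DAS28(CRP) by the final Dose Response Model at Week 12".

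Appendix 8 has a convergence fallback for the MMRM. For the dose-response models it asks only for a plot of residuals against fitted values. No bound, log-parameterisation, admissibility check or rule for a failed fit is given.

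**The concern.** A negative ED50 is not a dose. In the 3-parameter model the denominator Dose + ED50 then reaches zero at a positive dose, and the curve has a pole there. Nothing in the stated rules prevents such a fit from winning on AIC, because AIC sees only the residual sum of squares. The residual plot cannot reveal the fault: subjects exist only at 0, 45, 90 and 180 mg, where the fitted values look ordinary.

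The SAP synopsis says that all decisions on the final analyses are made before unblinding. A negative ED50 appears only afterwards. The analyst must then print an impossible value or improvise. Even when the point estimate is sensible, the bootstrap interval for ED50 can be built partly from impossible replicates.

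**Working it through.** **Inputs from the documents.** Protocol 4.1: "Approximately 40 subjects will be randomized into the study (10 subjects in each treatment groups". Protocol 9.2: "1:1:1:1 proportion to receive GSK3196165 doses of 45 mg, 90 mg, 180 mg or placebo". Protocol 9.4.4: "The dose response analyses will be performed on the change from baseline in DAS28(CRP) at Week 12". The models, starting values and AIC rule come from SAP 8.2.2.1.

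**Assumed inputs.** The documents give no effect size or SD for this endpoint, because the sample size rests on feasibility. I took an SD of the Week 12 change of 1.0 to 1.2 and a range of true shapes.

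**The plan's own figure.** The only precision figures for arms of 10 are the exact safety intervals in Protocol Table 4. Clopper-Pearson limits for 1, 2 and 3 events in 10 reproduce them: 0.3-44.5%, 2.5-55.6% and 6.7-65.2%. No operating characteristic is stated for the dose-response analysis.

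**Step 1: when ED50 turns negative.** Write the effect over placebo as e(d) = Emax × d/(d + ED50). Then e(45)/e(90) = (90 + ED50)/[2(45 + ED50)]. This is below 1 for ED50 > 0, exactly 1 at ED50 = 0, and above 1 for ED50 between -45 and 0. A 45 mg mean that happens to exceed the higher-dose means therefore pulls ED50 below zero. With SD 1, the difference between two arm means has standard error √(2/10) = 0.45, so this ordering is common when the true curve is flat above 45 mg.

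**Step 2: worked example.** Arm means 0, -1.0, -0.8, -0.9, SD 1, 10 per arm; within-arm sum of squares 4 × 9 × 1 = 36. AIC = 40 ln(RSS/40) + 2k.
- Linear (k = 3): slope = -66.375/17718.75 = -0.00375 per mg. RSS = 36 + 10 × 0.3789 = 39.79, AIC = 5.79. Effect at 45 mg: -0.17.
- Emax, unrestricted (k = 4): ED50 = -8.08, Emax = -0.80, E0 close to 0. Fitted values at 45, 90 and 180 mg: -0.98, -0.88, -0.84. RSS = 36 + 10 × 0.0107 = 36.11, AIC = 3.90. Emax wins.
- Between doses: at 5 mg, -0.80 × 5/(5 - 8.08) = +1.30; at 10 mg, -0.80 × 10/(10 - 8.08) = -4.17.
- Emax with ED50 held to 1.8-270 mg: the estimate lands on 1.8. RSS = 36 + 10 × 0.0238 = 36.24, AIC = 4.05, still below linear. Effect at 45 mg: -0.88.

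**Step 3: how often.** Simulated trials, unrestricted least squares from the SAP starting values, 3-parameter Emax against linear, SD 1.0 to 1.2:

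| True shape | ED50 < 0, among trials where Emax beats linear | ED50 < 0, among all trials |
|---|---|---|
| Flat | about 70-90% | 6-8% |
| ED50 45 mg, Emax -1.2 | about 40-50% | 13-16% |
| ED50 20 mg, Emax -1.2 | about 40-50% | 23-29% |
| Plateau of -0.9 at all doses | about 60-70% | 37-45% |

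For a true ED50 of 45 mg and a 180 mg effect of 1.5 SD, the first share falls to about 16%. With 8 per arm and the same ED50, it is 73%, 44% and 22% for effects of 0.5, 1.0 and 1.5 SD. Results shift by a few points with the optimiser; a Gauss-Newton run that also included the 4-parameter model gave 12% of all trials for the flat case. When an effect exists, nearly all negative fits (96-99% in the plateau and Emax shapes) have the pole between 0 and 45 mg. Under a flat truth about one fifth have it elsewhere.

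**Step 4: bootstrap.** Arm means 0, -0.7, -0.85, -1.0 give a sensible ED50 of about 30 mg. In a normal approximation to the bootstrap, about 24% of refits had ED50 < 0. The 2.5% limit was about -28 mg and the upper limit about 3.8 × 10⁸ mg.

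**Step 5: effect on the 45 mg estimate.** RMSE of the 45 mg effect at SD 1.0, rules as written against bounded ED50: 0.54 to 0.48 for a plateau of -0.9, and 0.46 to 0.43 for ED50 45 mg. For a flat truth it was 0.27 to 0.22.

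**Step 6: what a bound does.** With ED50 restricted to positive values, the share of selected Emax fits lying at the lower edge is about 86% (flat) and 64%, 39% and 16% (ED50 45 mg; 0.5, 1.0 and 1.5 SD).

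**The case against.** The SAP is silent on bounds; it does not prescribe an unbounded fit. It defines ED50 as a dose, offers its starting values only as examples, and notes in the display list that a statistician selects the final model. A negative ED50 would be noticed. The models are labelled exploratory, no hypothesis is tested, and the MMRM supplies the dose-placebo contrasts separately. All of this stands and limits the weight of the point. It does not supply a rule: selection is fixed as smallest AIC, and nothing says what to do with an impossible winner.

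A reader might infer several stronger things that the documents do not support:
- *That most trials would end this way.* The high shares are conditional on Emax beating linear; the last column of the table is lower throughout.
- *That the predicted responses fail.* Predictions and differences at the four studied doses stay finite. In the example the unrestricted fit gives -0.98 at 45 mg against an observed -1.0, closer than the bounded -0.88.
- *That the 45 mg effect would be badly understated by falling back to a straight line.* That gives an RMSE of 0.66-0.83 against about 0.50 with bounds, for plateaus of -0.9 to -1.2. But the SAP contains no such fallback, so this is not the plan's behaviour. Under a flat truth the fallback does better than bounds (0.14 against 0.22).
- *That Figure 2.4 will show a pole.* This depends on whether it draws a continuous curve. The figure shell is not in the documents, and the text asks for predictions at each dose.
- *That the 4-parameter model is worse still.* With ED50 negative and B not an integer it cannot be evaluated, so the issue there is a failed fit with no rule. It was simulated only with ED50 and B positive, and was then chosen in roughly 1-7% of trials.
- *That a 45 mg mean merely equal to the higher-dose means gives a negative ED50.* An exact plateau gives ED50 = 0.

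**Conclusion.** The point holds in a limited form. Following the stated fit, AIC and bootstrap steps can yield a negative ED50, an Emax that cannot be interpreted, and invalid intervals for both. In arms of 10 this is not rare: roughly one trial in seven for a true ED50 of 45 mg, and about two in five for a plateau of -0.9. The sizes rest on an assumed SD of 1.0 to 1.2, assumed true curves, and reading the SAP's silence as no restriction; they shrink as the effect grows. The gain in accuracy at 45 mg from bounding is modest. The main reason to change is that two reported parameters and their intervals would otherwise be meaningless, with no rule agreed before unblinding. The primary PK and safety analyses and the MMRM are untouched.

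**What to change.** In SAP 8.2.2.1:
- Constrain ED50 to a stated positive range, by a BOUNDS statement (for example 1.8 to 270 mg, which is 1% to 150% of the top dose) or by estimating log(ED50) with stated limits. Constrain B to a stated positive range.
- Apply the same constraints in the original fit and in every bootstrap replicate.
- Compute AIC from the constrained fit and keep fits that lie on a bound.
- Report how many of the 10,000 replicates lie on a bound.
- When ED50 is on a bound, report it as below or above that limit, without a two-sided interval.
- State the rule for non-converged fits, in the original data and in replicates.

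The cost is a few lines of text and a small change to the program. There is a real downside. The limits are a convention with no source in the documents, and many selected fits will sit on the lower one, so ED50 will often be reported only as an inequality. With four dose levels and 10 subjects per arm, that is a fair statement of what the data can show.
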